Intravenous lidocaine has an off label indication as analgesic and has good evidence for use in other areas such as colorectal surgery, trauma and orthopedics. Lidocaine infusions have a strong record of safety with relatively benign adverse side effects. Although data is promising, there is little established evidence of perioperative lidocaine infusions in renal transplant populations.

Transverse abdominis plane (TAP) blocks have emerged as a significant regional technique in the application of multimodal analgesia for abdominal surgeries. Historically, TAP catheters are avoided due to concern about infection near the operative site in immunosuppressed transplant patients. Establishing intravenous lidocaine as an effective treatment option will allow physicians to avoid the side effects of opioids and the infection risks of TAP catheter blocks.

Aims:

1. To see if Lidocaine infusion is non-inferior to TAP catheters for postoperative pain control
2. To see if higher rates of complications arise from non-opioid techniques (infection rates from TAP catheters, anesthetic toxicity from lidocaine infusion)

Recruitment: Recruitment for this study will take place in the preop waiting area. During that time, the purpose and method of the study will be explained to the patient. Patients will be informed of risks, benefits, and alternatives to participation in the study and will have the opportunity to sign consent after review of documentation and having all questions answered.

Recruitment cannot be done prior to the preop area because transplant surgeries are not scheduled far in advance. The organ recipient is called into the hospital when a match is found. The research team will be notified as soon as possible when a renal transplant is scheduled to allow for maximum amount of time to obtain consent.

Inclusion: Single Kidney transplant, >18 years old

Exclusion: Long term use of opioids (e.g. Chronic pain patients), history of substance abuse
Local anesthetic allergy
Complicated surgical course

- Intraoperative damage to other organs e.g. bowel

IRB NUMBER: NCR202221

IRB APPROVAL DATE: 02/18/2021

- Return to OR within 72 hours
- Postoperative ventilation

Methodology

Groupings

Patients will be randomly allocated into 2 groups: Lidocaine + PCA (L group) and TAP + PCA (T group). A member of the research team will perform the randomization and will notify the surgeon and the anesthesiologist on the case. This study is not blinded.

Sample size

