The goal will be to recruit at least 55 patients for the Lidocaine group and 25 patients for the TAP block group for a total of 80 patients in all. Sample size for this study is based on information gained from a retrospective study of renal transplant patients. The aim is to demonstrate non-inferiority of lidocaine to TAP block where non-inferiority is defined as <10% difference in OME consumption (with a 95% confidence interval) between the groups.

Intervention

When a renal transplant case is posted to the OR schedule, the research team will be notified. A team member will then meet with the patient in the preop area to obtain informed consent. Once consent is obtained, the medical records of the patient will be screened for exclusion criteria. If the patient meets all criteria, they will be randomized to one of the two study groups.

The anesthesiologist and surgeon on the case will be informed immediately of the group assignment.

In addition to the treatments assigned to each group, all patients will receive the standard of care medications given pre-op, intra-op, and post-op. These medications include oral Tylenol, oral oxycodone as needed, IV morphine or hydromorphone as needed, ketamine as indicated, and Ondansetron as needed. All patients will receive a dilaudid PCA 0.5mg bolus Q10min postoperatively as standard of care.

Following the case, the research team will review the operative note and anesthesia postoperative note to identify any disqualifying surgical complications (injured bowel, patient remains intubated, complication requiring return to OR within 72 hours). If there are disqualifying complications, the anesthesiologist and the surgeon will be notified and the patient removed from the study. Any further treatment for postoperative pain will be per standard of care and the surgeon's discretion.

If there are no disqualifying surgical complications, the following orders for postoperative pain control will be placed per the patient's assigned group:

- Lidocaine (+PCA): 1.0-1.5 mg/kg/hour for 48 hours post-operatively.
- TAP (+PCA): 0.2% Ropivacaine at 6-10ml/hour for up to five days post-operatively.

Nursing will routinely record VAS scores for all patients per nursing standard of care.

The research team will review patient charts daily to obtain the VAS scores and total narcotics used at 12 hours, 24 hours, and 48 hours as well as any notes regarding complications.

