Signs of complications due to the treatment methods will be reason to terminate the study and remove that patient from the study. Possible risks are listed below. The surgical team may terminate these treatment modalities as soon as a complication is identified, and may inform the research team as soon as possible afterwards.

Measures:

Demographics (age, gender, race, ASA)

Pain metrics at 12, 24, 48 hours (Time zero is arrival in PACU)

IRB NUMBER: NCR202221

IRB APPROVAL DATE: 02/18/2021

- Oral morphine Equivalents
- VAS score

Duration of operation

Surgeon

Length of stay (date of operation to date of discharge)

Complications

- Sepsis requiring antibiotic therapy
- Acute rejection of transplant
- Local Anesthetic Systemic Toxicity
- Need for CVVHDF
- Opioid toxicity requiring naloxone
- Ileus

Risks:

Risk of lidocaine infusion: Lidocaine toxicity (lightheadedness, dizziness, visual disturbances, confusion, tinnitus, and perioral numbness/peripheral paresthesia)

Risk of TAP block: local infection, hematoma, poor placement leading to inadequate pain control

Endpoints:

- VAS score
- Total opiate usage in morphine equivalents

Expected outcome and significance:

It is expected that patients with patients receiving lidocaine infusion will have equivalent opioid consumption and pain scores compared to patients receiving TAP blocks in the first 48 hours after surgery. If lidocaine infusion is demonstrated to be non-inferior to TAP blocks, this would provide physicians with an alternative to TAP blocks in controlling post-surgical pain while reducing total opioid usage.

Timetable: 36 months

References

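### Removing randomized patients after a treatment complication loses their later outcomes for Aim 2 and can bias the Aim 1 opioid comparison in either direction

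*Combined protocol and SAP*

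**What the plan says.** The rule is in the last paragraph of Methodology, Intervention: "Signs of complications due to the treatment methods will be reason to terminate the study and remove that patient from the study". The next sentence points to the Risks section for the possible complications, so that list supplies the triggers, and they differ by arm:

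- **Lidocaine:** "Risk of lidocaine infusion: Lidocaine toxicity (lightheadedness, dizziness, visual disturbances, confusion, tinnitus, and perioral numbness/peripheral paresthesia".
- **TAP:** local infection, hematoma, or "poor placement leading to inadequate pain control".

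Aim 2 is "To see if higher rates of complications arise from non-opioid techniques (infection rates from TAP catheters, anesthetic toxicity from lidocaine infusion". The complications list under Measures includes "Local Anesthetic Systemic Toxicity". Under Groupings the plan states "This study is not blinded".

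Data come from daily chart review, which collects VAS scores and "total narcotics used at 12 hours, 24 hours, and 48 hours as well as any notes regarding complications". The lidocaine order runs for 48 hours; the TAP order runs "for up to five days post-operatively".

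The document does not define an all-randomized analysis population, follow-up after removal, handling of missing data, or a sensitivity analysis.

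**The concern.** Patients are removed for having the kind of event that Aim 2 sets out to compare. Removal comes after randomization, is judged with the assignment known, and has different triggers in each arm. The patients left are therefore no longer the groups that randomization formed.

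For Aim 1, the direction of the bias cannot be predicted:

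- If removed lidocaine patients are high opioid users, the lidocaine mean falls and a false non-inferiority claim becomes more likely.
- If TAP patients with failed analgesia are removed, the TAP mean falls and non-inferiority becomes harder to show.
- Similar removal in both arms could cancel.

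The plan gives no means of telling afterwards which of these occurred.

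For Aim 2, the triggering event may well be recorded, because complication notes are collected. Later events in the same patient would not be. A TAP patient removed for hematoma or poor placement could later develop an infection that is never counted. Because the TAP window is longer, a complication after 48 hours could also remove a patient whose OME and VAS data are already complete.

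The sentence is also unclear in itself: its first half could mean ending the whole trial or ending one patient's participation.

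**Working it through.** **Inputs from the document (Sample size section).** 55 lidocaine and 25 TAP patients, total 80 (the sum is right); non-inferiority margin of less than 10% in OME, with a 95% confidence interval. The SD, mean OME, power and expected removals are not given. The sample size therefore cannot be re-derived, and what follows is illustration.

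**Assumptions.** x = fraction of an arm removed; r = mean OME of removed patients divided by that of retained patients; coefficient of variation (CV) of OME 0.3 or 0.5; analysis on the log ratio with a two-sided 95% interval and margin ln(1.10).

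**Step 1: hidden shift.** Mean over all randomized patients = retained mean × [(1−x) + xr] = retained mean × [1 + x(r−1)]. Dropping the removed patients hides a relative shift of x(r−1).

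**Step 2: one patient.** One TAP patient is 1/25 = 4.0% of the arm; at r = 1.5 the shift is 4.0% × 0.5 = 2.0%. One lidocaine patient is 1/55 = 1.8%; the shift is 1.8% × 0.5 = 0.9%. The 55/25 split makes each TAP removal count more than twice as much.

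**Step 3: probability of declaring non-inferiority.** SE = √ln(1+CV²) × √(1/55+1/25), which is 0.0708 at CV 0.3 and 0.1139 at CV 0.5. With δ = [ln(1.10) − ln(analysed ratio)]/SE, the probability is that of a noncentral t (78 df, noncentrality δ) exceeding 1.991.

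- *Lidocaine-only removal, true excess 10%:* analysed ratio = 1.10/[1+x(r−1)]. Example at x = 5%, r = 1.5, CV 0.3: δ = ln(1.025)/0.0708 = 0.349, probability 5.3%.
- *TAP-only removal, arms truly equal:* analysed ratio = 1+x(r−1). Same example: δ = ln(1.10/1.025)/0.0708 = 0.997, probability 16.5%.

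| x | r | Shift | False non-inferiority, lidocaine-only removal: CV 0.3 / 0.5 | Correct non-inferiority, TAP-only removal: CV 0.3 / 0.5 |
|---|---|---|---|---|
| 0 | – | 0 | 2.5% / 2.5% | 26.4% / 12.8% |
| 2% | 1.5 | 1% | 3.4% / 3.1% | 22.1% / 11.1% |
| 5% | 1.5 | 2.5% | 5.3% / 4.0% | 16.5% / 8.9% |
| 10% | 1.5 | 5% | 10.0% / 6.2% | 9.5% / 6.0% |
| 10% | 2 | 10% | 26.4% / 12.8% | 2.5% / 2.5% |

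Allowing for the smaller number after removal changes each entry by less than 1 percentage point. Equal x and r in both arms gives no net shift.

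**Step 4: check with patient counts, arms truly equal.** Removing 5 of 55 lidocaine patients gives an apparent lidocaine-minus-TAP difference of 1/(1+(5/55)×0.5) − 1 = −4.3% at r = 1.5, and −8.3% at r = 2. Removing 3 of 25 TAP patients gives +6.0% or +12.0%. Doing both gives 1.06/1.0455 − 1 = +1.4%, or 1.12/1.0909 − 1 = +2.7%.

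**Step 5: Aim 2.** One uncounted event changes a type-specific complication rate by 1/25 = 4.0 percentage points in the TAP arm or 1/55 = 1.8 in the lidocaine arm.

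**The case against.** - **The loss of data is inferred.** The document never says that chart review stops or that removed patients leave the analysis, and the rule could be a loose way of describing an end to study treatment. This does not rescue the text. The Intervention section uses the same removal language for disqualifying surgical complications, which are listed as exclusions. Stopping the treatment is covered by a separate sentence, so removal from the study is an additional step.
- **Aim 2 is less exposed than Aim 1.** If the trigger is recorded, a per-patient rate of any complication is unaffected. This stands in part: the 4.0 and 1.8 points apply to type-specific rates. Aim 2 does name specific types, however, and a TAP infection after removal for another reason would be missed.
- **Nothing links lidocaine toxicity to higher opioid use.** This is true; only the TAP trigger has a documented link to pain control. With r below 1 the sign reverses (x = 10%, r = 0.5 gives a shift of −5%). That confirms that the direction is unknown.
- **The shift is in arithmetic means but the test is on the log scale.** If r is a ratio of geometric means, the shift is r^x − 1: 0.8%, 2.0%, 4.1% and 7.2%. False non-inferiority at CV 0.3 is then about 3.2%, 4.7%, 8.2% and 16%. The margin is most naturally read as a difference in mean OME, and with a common CV in the retained arms the two mean ratios coincide. The alternative shrinks the figures and leaves the conclusion.
- **Loss of complete 48-hour data after a late TAP removal is not stated.** That is correct; it is a possibility the wording leaves open.

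**Conclusion.** The concern holds. The rule as written is an open-label exclusion after randomization, with arm-specific triggers that include outcomes under study, and nothing elsewhere in the document corrects it. It needs to be changed, because follow-up that was never collected cannot be restored by analysis.

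The existence of the defect does not depend on assumptions; its size does. With x from 2% to 10% and r of 1.5 or 2, the hidden shift runs from 1% to the full 10% margin. At CV 0.3 this takes the false non-inferiority rate from 2.5% to between 3.4% and 26%, or cuts the chance of correctly showing non-inferiority from 26% to between 22% and 2.5%. If removals are rare, or alike in number and opioid use in both arms, the Aim 1 effect is small.

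**What to change.** Leave the sentence that lets the surgical team stop a treatment as it is. Replace removal from the study with wording such as:

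> Patients whose study treatment is stopped for a complication stay in the study. OME, VAS, complications and length of stay continue to be collected from routine chart review unless consent is withdrawn.

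In addition:

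- Count every triggering complication as an outcome.
- Analyse OME, VAS and complications in all randomized patients by assigned group, with an on-treatment analysis as support for the non-inferiority conclusion. The supporting analysis is good practice; retention and analysis by assigned group are what cure the defect.
- Report by arm how many patients stopped treatment for a complication, and why.
- Reconcile the two halves of the removal sentence so that it is clear whether the trial or one patient's participation is meant.

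The cost is a wording amendment, slightly more chart review and one further analysis. The data are already in the routine chart, so no extra visits are needed.

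### Aim 2 asks for the TAP catheter infection rate, but the only infection item under Complications is sepsis from any source, and whether an event leading to a patient's removal is counted is not stated

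*Combined protocol and SAP*

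**What the plan says.** All references are to the combined protocol and SAP.

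- **Aims, item 2:** "To see if higher rates of complications arise from non-opioid techniques (infection rates from TAP catheters, anesthetic toxicity from lidocaine infusion").
- **Background:** the reason given for past reluctance is that "TAP catheters are avoided due to concern about infection near the operative site in immunosuppressed transplant patients". Avoiding this infection risk is part of the stated case for lidocaine.
- **Measures, Complications:** six items. The only one about infection is "Sepsis requiring antibiotic therapy". The others are acute rejection, systemic local anesthetic toxicity, CVVHDF, opioid toxicity treated with naloxone, and ileus.
- **Risks:** local infection is named as a risk of the TAP block.
- **Intervention, data collection:** "The research team will review patient charts daily" for pain scores and narcotic totals at 12, 24 and 48 hours, "as well as any notes regarding complications". No end date is given for the complication part.
- **Intervention, TAP arm:** "0.2% Ropivacaine at 6-10ml/hour for up to five days post-operatively".
- **Intervention, removal:** "Signs of complications due to the treatment methods will be reason to terminate the study and remove that patient from the study". The text does not say whether the event is then counted.
- **Groupings:** "This study is not blinded".
- **Endpoints:** VAS score and opioid use only.

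**The concern.** Aim 2 names two complication rates. Lidocaine toxicity has a corresponding line in the Complications list. Catheter infection does not: the hazard described in the Background and Risks is local, while the listed measure is systemic and not tied to the catheter. An analyst who tabulates the list as it stands would answer this half of Aim 2 with a different outcome.

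The removal rule adds a second uncertainty. A patient with a catheter-site infection is likely to be one who shows signs of a treatment complication, so the plan's silence on counting falls on the patients who would supply the Aim 2 numerator.

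At stake is the safety half of the argument for lidocaine over TAP catheters. A report of no sepsis in the TAP arm could be read as no catheter infections, and a sepsis from another source could be read as a catheter complication.

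**Working it through.** The plan states no infection rate, and no power or sample size for Aim 2, so there is no figure to reproduce. The check is first of the text, then of what one case does to the result.

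**Step 1. Which events Aim 2 wants and which the list counts (TAP arm).**

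| Event | Wanted by Aim 2 | Counted by the sepsis item |
|---|---|---|
| Catheter-site infection, no sepsis | Yes | No |
| Catheter-site infection with sepsis treated with antibiotics | Yes | Yes |
| Sepsis from another source, treated with antibiotics | No | Yes |

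The two definitions agree only in the middle row. The first row makes the listed rate too low and the third makes it too high, so the direction of the net error cannot be known in advance.

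**Step 2. Effect of one case.** Input: 25 TAP patients (Sample size), taken as the number analysed. Intervals are exact (Clopper-Pearson), two-sided 95%. For zero events the upper limit is 1 − 0.025^(1/n).

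- One non-septic site infection and no sepsis. Aim 2 rate: 1/25 = 4.0% (0.1% to 20.4%). Listed rate: 0/25, upper limit 1 − 0.025^(1/25) = 13.7%.
- One sepsis from another source and no site infection. The figures swap: the list gives 1/25 = 4.0%, while the Aim 2 rate is 0/25.
- One site infection, and the patient is removed from both numerator and denominator. The rate becomes 0/24, upper limit 1 − 0.025^(1/24) = 14.2%. The plan does not say this would be done; it is one reading that the silence allows.

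**Step 3. Is a case likely to arise?** The documents give no local infection risk, so p below is an assumption. The chance of at least one case in 25 is 1 − (1 − p)^25:

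- p = 1%: 22%
- p = 2%: 40%
- p = 5%: 72%
- p = 10%: 93%

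Across most of this range, at least one event that needs a defined place in the record is a realistic prospect.

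**Step 4. Precision once the item is added.** 0/25 leaves an upper limit of 13.7%, and 2/25 = 8.0% has an interval of 1.0% to 26.0%. For a wound or site infection item in the lidocaine arm (55 patients), 0/55 leaves 1 − 0.025^(1/55) = 6.5%. The change makes the count answer the right question; it does not make it precise.

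**The case against.** The best defence is that local infection is not overlooked. It is named under Risks, the removal rule points to that list, and the research team itself reads charts daily for complication notes of any kind, which is wider than the six listed items. The list is not said to be exhaustive. This stands: the gap is the lack of a defined outcome, and one cannot infer that local infections would go unrecorded. Free-text notes with no definition or tabulation rule, in an open-label trial, still do not give a reproducible rate.

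Three stronger readings are tempting and are not supported.

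- *Infection surveillance stops at 48 hours while the catheter stays in.* The 12, 24 and 48 hour times belong to pain scores and opioid use. No such limit is placed on complications, and length of stay already requires data to the discharge date. Only the absence of a stated window can be claimed, so the share of catheter time after 48 hours does not measure missed infection.
- *The undercount can be sized by assuming what fraction of local infections become septic.* It cannot, because the item would count sepsis from any source.
- *Events are discarded when a patient is removed.* The plan does not say so; it is silent.

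It is also fair to say that the other complication items lack criteria and windows, that complications are not among the Endpoints, and that 25 patients cannot settle an infection question. These points limit the priority of the finding. They do not answer it: the other items lack detail, whereas here the listed measure is a different outcome from the one the aim names.

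**Conclusion.** The point holds in a limited form. The Complications list, tabulated as written, cannot give the catheter infection rate that Aim 2 asks for; it gives a sepsis rate from any source. The plan also leaves open whether an event that leads to a patient's removal is counted. The unstated complication window is a secondary gap.

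The size is one case in 25: a move between 0% and 4.0%, in either direction, within intervals that are wide in any event. This assumes 25 TAP patients analysed and literal use of the list. The chances in Step 3 rest on assumed risks and only illustrate that a case is plausible.

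The missing infection item does not touch Aim 1, the opioid non-inferiority margin or the listed Endpoints. The removal rule may also bear on the pain data, but that is a separate question. The change should be made because a stated aim depends on it and it is cheap, though it ranks below any defect in the Aim 1 comparison.

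**What to change.** 1. Add two items to Complications: catheter-site infection (TAP arm) and, recorded separately, surgical wound or site infection (both arms), each with or without sepsis. Keeping them apart preserves the catheter-specific rate and gives one infection measure that can be compared between arms. Set the criteria before enrolment and base them on findings recorded in the chart, because the study is not blinded. Sepsis can stay as its own item.
2. State that a patient removed for a treatment complication stays in the Aim 2 numerator and denominator of the assigned arm. This concerns counting only and does not change when treatment stops.
3. State that the existing daily review for complications runs through discharge in both arms, since the TAP infusion may continue past the last pain reading.

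Cost: two chart fields, a few sentences of definition, and a somewhat longer review for patients who stay beyond 48 hours. Charts are already needed to discharge for length of stay, and no visits or procedures are added. Infections that first appear after discharge would still be missed, and the report should say so and acknowledge the low precision.

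### Hematoma and poor placement are named as TAP risks but have no item in the Complications list, so Aim 2 may under-count TAP harm

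*Combined protocol and SAP*

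**What the plan says.** Aim 2 is "To see if higher rates of complications arise from non-opioid techniques". Its parenthesis gives catheter infection for TAP and anesthetic toxicity for lidocaine.

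Under Measures, the Complications list has six items: "Sepsis requiring antibiotic therapy", acute rejection, "Local Anesthetic Systemic Toxicity", CVVHDF, "Opioid toxicity requiring naloxone", and ileus. The Risks section that follows gives toxicity for lidocaine and, for the other arm, "Risk of TAP block: local infection, hematoma, poor placement leading to inadequate pain control".

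Two passages in Intervention govern what happens to an event. The daily chart review collects pain scores and opioid use "as well as any notes regarding complications". Then: "Signs of complications due to the treatment methods will be reason to terminate the study and remove that patient from the study". The next sentence refers the reader to the Risks list for the complications in question.

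Sample size plans at least 55 lidocaine and 25 TAP patients. Groupings states that the study is not blinded.

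**The concern.** A comparison of complication rates needs events defined in advance and counted in the same way in both arms. Two events that the protocol itself attributes to TAP are not on the list of events to be measured. The plan has a source for them (chart notes) and a consequence (possible removal), but no rule that turns them into a count.

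In an unblinded trial, this leaves the decision on which unlisted events count to people who know the arm. With 25 TAP patients, one event more or less moves the observed rate by 1/25 = 4 percentage points. The Background argues for lidocaine partly because it avoids harms of TAP catheters, so incomplete counting of those harms weakens what Aim 2 can say.

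**Working it through.** The plan states no complication rate, tabulation rule or precision target for Aim 2, so there is no figure to reproduce. The check is a comparison of the lists, followed by the scale of what could be missed.

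**1. Risks against Complications.**

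| Named risk | Arm | Closest Complications item |
|---|---|---|
| Toxicity | Lidocaine | "Local Anesthetic Systemic Toxicity" |
| Local infection | TAP | "Sepsis requiring antibiotic therapy", so only if it becomes that severe |
| Hematoma | TAP | None |
| Poor placement | TAP | None; its effect on pain would show in VAS and opioid use |

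Two of the three TAP risks have no item. The toxicity item is not exclusive to lidocaine: the TAP arm receives ropivacaine, also a local anesthetic.

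**2. What the plan does with an unlisted event.**

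- It may be written in the chart and picked up by the daily review. Whether it is then classified and counted is not stated.
- It may trigger removal, because the removal rule points to the Risks list, which includes both events. Whether a removed patient still contributes to Aim 2 is not stated.
- A hematoma that requires a return to the operating room within 72 hours is a disqualifying complication under Exclusion and Intervention, in either arm. Again, nothing says whether the event is counted.

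**3. Scale.** Inputs: n = 25 TAP patients (Sample size) and p, the rate of an unlisted TAP event, which the documents do not give and which is assumed here. Expected events = 25p; P(at least one) = 1 − (1 − p)^25.

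| Assumed p | Expected events | P(at least one) |
|---|---|---|
| 1% | 0.25 | 1 − 0.99^25 = 0.222 |
| 2% | 0.50 | 1 − 0.98^25 = 0.397 |
| 5% | 1.25 | 1 − 0.95^25 = 0.723 |
| 10% | 2.50 | 1 − 0.90^25 = 0.928 |

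These are chances that an event occurs, not that it goes uncounted.

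**4. Precision if the events are counted.** For zero events, the exact two-sided 95% upper limit is 1 − 0.025^(1/n). For 0 of 25 it is 1 − 0.025^(1/25) = 13.7%. For 0 of 55 it is 1 − 0.025^(1/55) = 6.5%. For 1 of 25 the exact interval is 0.1% to 20.4%.

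**The case against.** The strongest reply is that the plan does not ignore these events. Chart review is open-ended, and nothing says that a noted hematoma goes uncounted. This stands against a stronger reading. A reader might infer that a TAP patient with a hematoma or misplaced catheter will be tabulated as complication-free, and that all such events will be missing from the results. The documents contain no tabulation rule and no complication-free category, and removal is a documented path for such a patient. What remains is that neither path leads to a stated count.

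A reader might also infer that the list is slanted towards TAP, because the lidocaine risk is counted and the mechanical TAP risks are not. That is not established, since the toxicity item covers both arms.

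Poor placement is described through its result, inadequate pain control, which the VAS and opioid endpoints measure at 12, 24 and 48 hours. This stands for patients who remain in the study, and it argues against a TAP-only item for inadequate analgesia blamed on placement. In an unblinded trial such an item would be subjective and one-sided.

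Finally, the parenthesis in Aim 2 names only infection and toxicity. However, the aim itself speaks of complications generally, and the Complications list already goes beyond the parenthesis with rejection, CVVHDF and ileus. This objection supports saying that Aim 2 may under-count TAP harm rather than that it does; it does not remove the gap.

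**Conclusion.** The concern holds in a limited form. Hematoma and poor placement are named TAP risks without a Complications item, and the plan does not say how free-text notes or removed patients enter Aim 2. TAP harm may therefore be under-counted. The size cannot be determined from the documents; the 22% to 93% chance of at least one event among 25 TAP patients rests entirely on assumed rates of 1% to 10%. The documents do not show that events will certainly be lost, or that the list as written biases the comparison towards TAP. Even with complete counting, the TAP arm is too small for more than a descriptive statement about rare harms.

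**What to change.** - Add an item for abdominal wall or wound hematoma to the Complications list, taken from the planned daily chart review and recorded the same way in both arms.
- State that listed complications are counted for every randomised patient, by randomised arm, including events that lead to removal. Without this, a new item alone would not ensure that the events are counted.
- Report counts with exact 95% confidence intervals per arm.
- If technical failure is to be recorded, use an objective item with an equivalent in both arms, such as assigned technique stopped early, with the reason (catheter dislodged or misplaced; infusion stopped). Leave inadequate analgesia to the VAS and opioid endpoints.
- Reconcile the Risks list, the Complications list and the removal rule, so that it is clear which events are measured and what happens to the data of a patient who has one. This concerns counting only, not when treatment should stop.

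The cost is a few lines in the protocol and on the data form, plus continued chart review for complications in removed patients; no new visit or procedure is needed. The downsides are that some hematomas will be surgical rather than catheter-related, which is why both arms are counted, and that the intervals will be wide.
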